 - 4.1. Participants will receive a communication (**Appendix D**) via email and or SMS text messages automated through REDCap from the study team 1-2 weeks prior to the time points indicated in table 2 to complete the survey responses noted
 - 4.2. Participants will have the option for compensation to be sent to them via an approved VA modality at the conclusion of all surveys
- 5. Qualitative interviews
 - 5.1. Study staff will use maximum variation sampling to select a subset of participants to invite for qualitative interview
 - 5.2. Research staff will set up a time to speak with the participant either in person at VAPORHCS, or over an agreed upon and VA-approved remote video modality (i.e. VA Video Connect, although in specified circumstances other video conferencing applications such as Apple Facetime, Facebook Messenger, Skype, Zoom, Cisco WebEx, or Google Hangouts may be used. Public facing applications will not be used).
 - 5.2.1. Participants will be informed that certain third-party video applications may introduce additional privacy risks.
 - 5.2.2. Research staff will use all available encryption and privacy modes.
 - 5.3. Informed consent from interview participants will be collected verbally and will be audio recorded
 - 5.4. Interviews will be audio recorded and will last between 45-60 minutes using the interview guide (**Appendix C**)
 - 5.5. Participants interviewed in-person will receive compensation at the conclusion of the interview at the hospital agent cashier.
 - 5.6. Participants interviewed remotely will receive compensation at the conclusion of the interview via an approved VA modality.
- 6. Data analysis
 - 6.1. Conduct quantitative data analysis of survey data to examine descriptive statistics and distributions for variables at each of their timepoints.
 - 6.2. Conduct qualitative content analysis with a directed grounded theory approach with interview data.
- 7. Dissemination Activities
 - 7.1. Review quantitative and qualitative analysis and develop publications
 - 7.2. Review data and use to develop future larger RCT

References & Literature Cited

1. *2019 National Veteran Suicide Prevention Annual Report*. Office of Mental Health and Suicide Prevention; U.S. Department of Veteran Affairs https://www.mentalhealth.va.gov/docs/data-sheets/2019/2019_National_Veteran_Suicide_Prevention_Annual_Report_508.pdf

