2. **Surveys.** Participants will complete surveys online at baseline (before and after the training) and at monthly follow-up (1, 2, 3, 4, 5, and 6 months). Surveys contain standard items and scales to collect self-reported information and attitudes. This includes sociodemographic characteristics, knowledge,

self-efficacy, social norms, stigma, behavioral intentions, use of gatekeeper behaviors, suicidal ideation, and help-seeking. See **Appendix B** for baseline survey. Follow-up surveys will contain a subset of baseline survey measures—see **Table 2** below for a timeline of measures.

3. **Interviews.** A small subgroup of study participants (n = 15) who were assigned to the intervention group will be invited to participate in an interview to take place approximately one-month post-intervention. Interviews will include questions on feasibility and acceptability of the social media ad campaign and on PsychArmor S.A.V.E. See Qualitative Data Collection section below for a more detailed description and **Appendix C** for the interview guide. Interviews will be audio-recorded and written notes will be recorded by the interviewer.

Potential Difficulties, Limitations, and Alternatives. A potential difficulty is struggling to recruit enough interested and eligible participants online. We will monitor recruitment progress on a weekly basis using a module in our data management software (OHSU instance of REDCap), which allows real-time monitoring of progress against targets. If we do not meet a minimum recruitment milestone of 50 participants in three weeks, the research team may consult with a recruitment specialist at the Oregon Clinical and Translation Research Institute and OHSU's Strategic Communications social media team about adding recruitment strategies in accordance with NIH guidelines,⁵² and/or placing advertising on additional social media platforms.

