Given the 6-month length of follow-up, another potential difficulty is sample retention. To promote sample retention we will employ methods with empirical validation in increasing online study response and retention rates: 1) minimizing survey burden, 2) specifying survey time estimates, and 4) sending reminder emails, texts, and small messages of appreciation to study participants.⁵³ Of note, prior research among military personnel suggests that survey retention is higher in web-based surveys than paper-based surveys.⁵⁴ We will also employ modest financial incentives. In the case of incomplete follow-up, reminders will be sent with use of email and additional modalities (e.g., text message) as consented to by the participant.

Timetable for study. The project timeline is presented in the **Table 1**. Special consideration was made for the time required to: develop the social media ad campaign (3 months), setup study infrastructure including REDCap data collection and management system and a study website containing integration of the two study arms (4 months), and conduct recruitment (2.5 months) and participant follow-up (6 months). During the dissemination and next steps phase, we will prepare a grant application for the larger-scale RCT and prepare the study products noted above.

Activity	Table 1		Year 1		Year 2			
	Quarter		Q 1	Q 2	Q 3	Q 4	Q 1	Q 2
Start-up, IRB, and hiring	X							
Social media ad development		X						
Study infrastructure setup		X	X					
Online recruitment			X					
Baseline & follow-up assessments					X	X		
Interview training			X					
Interview conduct				X				
Qualitative data analyses						X	X	
Quantitative data analyses						X	X	
Dissemination/Next steps							X	

Measures. A timeline of measures is presented in **Table 2** and described further below.

Table 2: Summary of Study Measures

Timepoint(s)	Measure	Main Function	Aim(s)
0	Numbers screened, eligible, and enrolled per week; proportion eligible who enroll	Feasibility	1

PT, 1, 2, 3, 4, 5, 6	Retention rate; survey completion rate; exposure	Feasibility	1
PT	Completion of training; satisfaction; usability	Acceptability	2
0	Background characteristics	Descriptive data	1, 2
0, PT, 2, 4, 6	Intention to use of gatekeeper behaviors	Mechanisms of action	2
0, PT, 2, 4, 6	Knowledge; stigma; self-efficacy; social norms	Mechanisms of action	2
0, PT, 1, 2, 3, 4, 5, 6	Gatekeeper behaviors; suicidal ideation; help-seeking, social support	Measurement characteristics	2

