1	Semi-structured interview about social media ads and PsychArmor S.A.V.E.	Feasibility and acceptability	1, 2

0=pre-training (baseline); PT=post-training (immediately after); 1=1-month follow-up, 2=2-month follow-up, etc.

Feasibility: We have selected feasibility measures most appropriate for a pilot intervention and previously used to assess online interventions.^{55, 56} These measures address each stage of the project including screening (number screened/eligible per week), recruitment (number enrolled per week), randomization (proportion of eligible who enroll), cross-contamination (number of control group participants who report taking PsychArmor S.A.V.E. training), retention (i.e., loss to follow-up), and assessment process (survey completion rates).

Acceptability: For acceptability, we will use a combination of three measures: completion of the training, satisfaction (measured using the validated eight-item Client Satisfaction Questionnaire (CSQ-8),⁵⁷ and the System Usability Scale (SUS) along with a single item usability rating that is highly correlated ($r=0.82$) with the SUS.^{58, 59}

Background Characteristics: This will include standard items on age, gender, race/ethnicity, education, marital status, zip code (rurality), occupation, military experiences, social media platform use, frequency of social contact with Veterans, social network size, and VA and other health service use.

Intentions to Use Gatekeeper Behaviors: Suicide prevention training research has shown that behavioral intention has a direct effect on actual behavior and also mediates the relationship between attitudes and actual behaviors.⁶⁰ Thus, we have chosen a three-item scale to assess behavioral intentions to use core skills learned in gatekeeper training (recognizing gatekeeper opportunities, inquiring about suicidal ideation, and making a professional referral). In research conducted by our research team and others, scales of intentions to use gatekeeper behaviors have shown adequate internal reliability.^{14, 60}

Knowledge: The 12-item short form of the Literacy of Suicide Scale (LOSS) measures knowledge about suicide. A total literacy score can be calculated as the percent of all correct items.⁶¹

Stigma: The 16-item short form of the Stigma of Suicide Scale (SOSS) measures public stigma towards individuals who die by suicide. It shows reliability and validity in community-based samples.⁶²

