Self-Efficacy: A four-item scale we have previously used to assess confidence to use gatekeeper skills. This scale has shown adequate internal reliability in our prior trial of gatekeeper training.¹⁵

Social Norms: A two-item scale we have previously used that assesses the degree to which one believes that most people do seek (descriptive norm) or should seek (injunctive norm) professional care if having suicidal thoughts. Items show adequate internal reliability.^{14, 48}

Gatekeeper Behaviors: Three items that assess actual self-reported frequency of: 1) recognizing gatekeeper opportunities ("In the last month, how many people have you encountered that you suspected were in an emotional crisis?"); 2) inquiring about suicidal ideation ("...how many times did you directly ask such a person if they were having suicidal thoughts?"); and 3) making a professional referral ("...how many times did you directly refer such a person to mental health or other professional treatment?"). Items are derived from outcome measures in prior gatekeeper training trials.⁶³

Suicidal Ideation: The Depression Symptom Index Suicidality Subscale (DSI-SS) is a four-item measure of suicidal ideation over the past two weeks with strong psychometric properties.^{64, 65}

Help-Seeking: The Actual Help-Seeking Questionnaire (AHSQ) consists of four dichotomous items asking whether in the last month the respondent has sought help for a mental health problem.⁶⁶

Social Support: The Patient-Reported Outcomes Measurement Information System (PROMIS) short form – Emotional Support 4a is a four-item measure of emotional support.⁶⁷

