With the exception of ZIP Codes needed to assess rurality, all other identifiers will be removed from the dataset prior to export from REDCap. Data containing the ZIP Code identifiers may be stored on OHSU Box (OHSU.box.com), an institution supported, cloud-based file sharing and storage option with added protections in place for OHSU confidential and restricted data or protected health information. Box.com adheres to the highest industry standards for security and is compliant with HIPAA requirements as well as federal government agency requirements such as the Department of Defense. All files uploaded to Box are encrypted at rest using 256-bit AES encryption, and further protected by an encryption key-wrapping strategy. The company also offers customer-managed encryption keys. Box provides you with in-depth, unchangeable audit logs, user permission options and restrictions, and organization-wide controls and permissions. OHSU and Box have entered into a Business Associate Agreement, including a data use agreement, that meets all OHSU privacy, confidentiality, and information technology policy compliance requirements. This includes requirements for software applications to use specific login IDs, passwords, OHSU-approved encryption, audit software, and reporting requirements to privacy officers when becoming aware of any users not in compliance.

Communications with participants will include invitations and reminders for follow-up surveys, reminders and notifications about incentive payments, and for a subset of participants, invitations to participate in an interview and the interview itself (**Appendix D**). Study invitations and reminders will be sent by email or SMS text message to study participants. For these communications, we will take special precautions to preserve privacy, confidentiality, and data security. These communications will not contain PII/PHI. Any email communication that does contain PII/PHI will be encrypted and sent via Azure Rights Management Services (RMS).

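### Follow-up surveys are sent out 1-2 weeks before they fall due with no completion window, so the one-month recall items at month 1 can include time before the training

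*Combined protocol and SAP*

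**What the plan says.** Step 4.1 of the Step-by-Step Guidance has participants receive an email or text message "from the study team 1-2 weeks prior to the time points indicated in table 2 to complete the survey responses noted". The section on protection against risk describes the correspondence in similar terms: "Communications with participants will include invitations and reminders for follow-up surveys". The section on potential difficulties adds that reminders go to people whose follow-up is incomplete.

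Under Measures, the first gatekeeper-behaviour item reads "In the last month, how many people have you encountered that you suspected were in an emotional crisis", and the other two items continue the same stem. The help-seeking questionnaire has four yes/no items "asking whether in the last month the respondent has sought help for a mental health problem". The suicidal-ideation scale differs: it "is a four-item measure of suicidal ideation over the past two weeks".

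Table 2 lists "Gatekeeper behaviors; suicidal ideation; help-seeking, social support" in one row, collected at baseline, immediately after training (PT) and at months 1 to 6. Its stated function is measurement characteristics. The legend defines the codes as "PT=post-training (immediately after); 1=1-month follow-up, 2=2-month follow-up, etc".

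The document does not say when a survey link becomes active, when it expires, or which event starts the month count. Appendices B (survey) and D (participant messages) are listed, but their content is not in the document.

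**The concern.** A one-month look-back at one month after training covers only post-training time if the answer comes no earlier than the due date. Step 4.1 invites an earlier answer. Someone who responds at once reports partly on days before seeing either video, when the two randomised arms should behave alike.

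Month 1 matters because it is the first wave that can show post-training behaviour. At PT the participant has only just finished the video, so the whole look-back precedes the training.

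Behaviour and help-seeking data have one main purpose here. The Specific Aims list measurement properties of key outcomes, for use in designing the larger trial, among three key deliverables. Month-1 values pulled toward baseline would understate early change and any arm difference in what is handed on.

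**Working it through.** The plan gives no figure for recall overlap, so there is none to reproduce.

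**Inputs from the document.** Message sent e = 7 or 14 days before the time point (step 4.1); recall of one month for behaviours and help-seeking, and two weeks for suicidal ideation (Measures); time points at months 1 to 6 (Table 2).

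**Assumptions.** Training on day 0; month and recall both 30 days; answer given d days after the message; constant event rate within each period; equal rates in the two arms before training.

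**Pre-training share at month 1.** The answer falls on day 30 - e + d and the recall starts 30 days earlier, on day d - e. The share is max(0, e - d)/30.

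- e = 7, d = 0: answered on day 23; 7/30 = 23%.
- e = 14, d = 0: answered on day 16; 14/30 = 47%.

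| Days from message to answer | Message 7 days early | Message 14 days early |
|---|---|---|
| 0 | 23% | 47% |
| 3 | 13% | 37% |
| 7 | 0% | 23% |
| 10 | 0% | 13% |
| 14 | 0% | 0% |

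If half answer on receipt and half at day 30 or later, the average share is 0.5 × 23% = 12% to 0.5 × 47% = 23%. With months of 28 to 31 days, the on-receipt range is 7/31 = 23% to 14/28 = 50%.

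**Effect on a difference in counts.** Pre-training days contribute equally to both arms, so the expected difference is the true monthly difference times (1 - share). On receipt it keeps 1 - 0.23 = 77% (7 days early) or 1 - 0.47 = 53% (14 days early) of its size.

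**Effect on a yes/no item.** Take assumed monthly help-seeking of 20% in control and 30% in intervention (neither figure is in the document). With constant hazards, -ln(0.80) = 0.223 and -ln(0.70) = 0.357.

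- 7 days early: 1 - exp[-(0.223 × 7/30 + 0.357 × 23/30)] = 27.8%, a difference of 7.8 points instead of 10.
- 14 days early: 1 - exp[-(0.223 × 14/30 + 0.357 × 16/30)] = 25.5%, a difference of 5.5 points.

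**Other waves and measures.** Month 2 answered on receipt has a recall starting on day 60 - 7 - 30 = 23 or 60 - 14 - 30 = 16, entirely after training; later waves start later still. The two-week ideation recall at month 1 starts on day 30 - 7 - 14 = 9 or 30 - 14 - 14 = 2, also after training. At PT the one-month recall is 100% pre-training.

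**The case against.** The strongest reply is that the harm is conditional. Step 4.1 does not say that the link is live when the message arrives. The messages include both invitations and reminders, and the unseen appendices may hold an opening date or an advance notice. This stands in part: a reader might infer that every month-1 survey reaches back before training, and the documents do not support that. The 23% and 47% figures need a live link and an immediate answer. But the stated purpose of the message is completion of the survey, and nothing in the protocol text prevents an answer on day 16 to 23.

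A second reply is that the consequence is limited. That is right. None of the four hypotheses uses behaviours or help-seeking, the follow-up analysis is descriptive by time point, and arm tests are named only for baseline values.

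Three further inferences go beyond the documents:

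- Month 1 is not the first scheduled measurement after training, because Table 2 also has these items at PT. It is the first that can reflect post-training behaviour.
- Events could be counted twice across waves: month 2 answered two weeks late (days 44 to 74) and month 3 two weeks early (days 46 to 76) share 28 days. This is an extreme pairing. A consistently early responder keeps roughly 30-day spacing, and no sum across waves is planned.
- A month-6 survey answered on day 180 - 14 = 166 might count as retained. The missing window leaves that open, but the documents give no basis for sizing an effect on Hypothesis 1.3.

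**Conclusion.** The concern holds in a limited form. Followed as written, step 4.1 allows the month-1 behaviour and help-seeking recall to include pre-training time: at most 23% to 47% of a 30-day look-back if answered on receipt, 12% to 23% on average if half do so, and none at day 30 or later. Any between-arm difference in counts is diluted by that share, always toward no difference. These sizes rest on a 30-day month, a constant event rate and a message that carries a usable link; the actual response delays are unknown.

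The damage is confined to month 1 and to what it tells the designers of the larger trial. It does not alter the tests of the four hypotheses as the plan describes them. It should still be corrected before data collection, because an early answer to an unanchored recall item cannot afterwards be split into pre- and post-training parts.

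**What to change.** Amend step 4.1 as follows:

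- Count months from the training date. Open each survey link on its due date (day 30, 60, ... 180) and close it when the next survey opens, with a stated closing date for month 6.
- Make any message sent 1-2 weeks ahead a notice without a link.
- Keep the completion date in the analysis file.
- State that the PT behaviour and help-seeking items are not post-training outcomes.

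Keep the existing one-month wording of the items. Rewording the month-1 stem to run from the training date would give a look-back of 30 to almost 60 days within this window, unlike the baseline item and the other waves. It would also change the survey, and step 1.2.2 sends substantive survey changes to the IRB.

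The change removes pre-training time from month 1. It does not remove all overlap between waves: answers on days 59 and 60 would share 29 recall days. If anyone later sums events across waves, the completion dates will be needed.

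The cost is a REDCap scheduling setting, a few protocol sentences and a matching check of the Appendix D messages. A few people who would have answered very early or very late may be lost, which bears slightly on retention.
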